16.3 Analysis Plan

The analysis for this trial will commence at planned time points (see 16.2) and at the time the patients have become evaluable for the primary endpoint. The Statistician and Study Chair will make the decision, in accord with ACCRU Standard Operating Procedures, availability of data for secondary endpoints (e.g., laboratory correlates), and the level of data maturity. It is anticipated that the earliest date in which the results will be made available via manuscript, abstract, or presentation format is when last patient has been followed for at least 6 months.

16.31 Primary Outcome Analyses:

- 16.311 **Definition:** The primary endpoint of this trial is the rate of overall metabolic response. A metabolic response is defined as a patient who has achieved an objective status of PMR or CMR at the end of cycle 8. All patients meeting the eligibility criteria who have signed a consent form and have begun treatment will

be evaluable for metabolic response, unless they are determined to be a major violation or are replaced in the safety analysis phase per Section 13.6. If the safety analysis determines that a reduction to the starting dose is warranted, only patients treated at the final dose level will be included when evaluating the decision rules in Sections 16.211 and 16.212. Patients treated at other dose levels will be summarized separately.

- 16.312 Estimation: The proportion of successes will be estimated by the number of successes divided by the total number of evaluable patients. Ninety-five percent confidence intervals for the true success proportion will be calculated according to the approach of Duffy and Santner.
- 16.313 Over Accrual: If more than the target number of patients are accrued, the additional patients will not be used to evaluate the stopping rule or used in any decision making processes; however, they will be included in final point estimates and confidence intervals.
- 16.32 Secondary Outcome Analyses
- 16.321 The complete metabolic response rate will be estimated by the total number of complete metabolic responses (CMR) divided by the total number of evaluable patients. All evaluable patients will be used for this analysis. Exact binomial 95% confidence intervals for the true complete metabolic response rate will be calculated.
- 16.322 Duration of response is defined for all evaluable patients who have achieved a response as the date at which the patient's objective status is first noted to be a CMR or PMR to the earliest date progression (PMD or PD) is documented. If a patient has not had disease progression, they will be censored on the date of their last disease assessment. The distribution of duration of response will be estimated using the method of Kaplan-Meier.
- 16.322 Progression-free survival is defined as the time from registration to the earliest date of documentation of disease progression (PMD or PD) or death due to any cause. If a patient is alive and has not had disease progression, they will be censored on the date of their last disease assessment. The distribution of progression-free survival will be estimated using the method of Kaplan-Meier.
- 16.323 Overall survival time is defined as the time from registration to death due to any cause. If a patient is still alive, they will be censored on the date of their last follow-up. The distribution of overall survival will be estimated using the method of Kaplan-Meier.
- 16.324 Adverse Events: All eligible patients that have initiated treatment will be considered evaluable for assessing adverse event rate(s). Adverse events will be assessed using CTCAE version 4.0 per Section 10.0. The maximum grade for each type of adverse event will be recorded for each patient, and frequency tables will be reviewed to determine patterns. Additionally, the relationship of the adverse event(s) to the study treatment will be taken into consideration.
- 16.33 Correlative Outcome Analyses: Due to the small overall sample size, the results of these analyses will be considered exploratory and hypothesis-generating in nature.
- 16.331 Biomarkers including intratumoral cell populations, genetic variability, serum cytokines, and T-cell activation will be evaluated both before and during treatment. Baseline values and changes in these parameters over time will be both graphically

and quantitatively summarized and explored. Standard paired comparisons methodologies (paired t-tests, Wilcoxon signed rank tests and Fisher's exact tests for interval, ordinal and nominal level data, respectively) will be used to assess changes in these variables before and after therapy. In addition, baseline values and changes over time in each measure will be explored in relation to clinical outcome to explore any differences between responders and non-responders and by depth of response (CMR vs. PMR) to identify potential biomarkers.

- 16.4 Early Safety Analysis: An early safety analysis will be performed after the first 6 patients have been accrued to the study at dose level 1 and observed for one cycle. If 2 or more of the first 6 patients experience a DLT as defined in Section 7.12, then the starting dose level will be adjusted and additional cohorts may be evaluated at dose levels -1 and -2 as described below. Accrual will be halted while evaluating each cohort in the early safety analysis.
- 16.41 Dose level +1: Six evaluable patients will be accrued onto dose level +1 and observed until they complete one cycle treatment. If 0 or 1 out of 6 patients experience a DLT, accrual will continue in the phase II portion at dose level 1. If 2 or more patients experience a DLT on dose level +1, the toxicity level for dose level +1 will be considered unacceptable and six additional patients will be treated on dose level -1.
- 16.42 Dose de-escalation to Dose level -1: If dose level +1 has an unacceptable level of toxicity, six evaluable patients will be accrued onto dose level -1. If 0 or 1 out of 6 patients experience a DLT on dose level -1, accrual will continue in the phase II portion at dose level -1. If 2 or more patients experience a DLT, the toxicity level for dose level -1 will be considered unacceptable and six additional patients will be treated on dose level -2.
- 16.43 Dose escalation to Dose level -2: If dose level -1 has an unacceptable level of toxicity, six evaluable patients will be accrued onto dose level -2. If 0 or 1 out of 6 patients experience a DLT on dose level -2, accrual will continue in the phase II portion at dose level -2. If 2 or more patients experience a DLT, the toxicity level for dose level -2 will be considered unacceptable and accrual to the study will be temporarily closed, evaluated and potentially amended.
- 16.5 Data & Safety Monitoring:
- 16.51 The principal investigator(s) and the study statistician will review the study at least twice a year to identify accrual, adverse event, and any endpoint problems that might be developing. The Mayo Clinic Cancer Center (MCCC) Data Safety Monitoring Board (DSMB) is responsible for reviewing accrual and safety data for this trial at least twice a year, based on reports provided by the MCCC Statistical Office.
- 16.52 Adverse Event Stopping Rules (to include all patients treated at the dose level determined in the early safety analysis): The stopping rules specified below are based on the knowledge available at study development. We note that the Adverse Event Stopping Rule may be adjusted in the event of either (1) the study re-opening to accrual or (2) at any time during the conduct of the trial and in consideration of newly acquired information regarding the adverse event profile of the treatment(s) under investigation. The study team may choose to suspend accrual because of unexpected adverse event profiles that have not crossed the specified rule below. Accrual will be temporarily suspended to this study if at any time we observe events considered at least possibly related to study treatment (i.e. an adverse event with attribute specified as "possible," "probable," or "definite") that satisfy one of the following:
- if 5 or more patients in the first 15 treated patients experience a grade 4 or higher non-hematologic adverse event at least possibly related to treatment.

- if after the first 15 patients have been treated, 30% of all patients experience a grade 4 or higher non-hematologic adverse event at least possibly related to treatment.

We note that we will review grade 4 and 5 adverse events deemed “unrelated” or “unlikely to be related”, to verify their attribution and to monitor the emergence of a previously unrecognized treatment-related adverse event.

- 16.6 Results Reporting on ClinicalTrials.gov: At study activation, this study will have been registered within the “ClinicalTrials.gov” website. The Primary and Secondary Endpoints along with other required information for this study will be reported [REDACTED]. For purposes of timing of the Results Reporting, the initial estimated completion date for the Primary Endpoint of this study is 3.5 years after the study opens to accrual. The definition of “Primary Endpoint Completion Date” (PECD) for this study is at the time the last patient registered has been followed for at least 6 months.
- 16.7 Inclusion of Women and Minorities
- 16.71 This study will be available to all eligible patients, regardless of race, gender, or ethnic origin.
- 16.72 There is no information currently available regarding differential effects of this regimen in subsets defined by race, gender, or ethnicity, and there is no reason to expect such differences to exist. Therefore, although the planned analysis will, as always, look for differences in treatment effect based on racial and gender groupings, the sample size is not increased in order to provide additional power for subset analyses.
- 16.73 The geographical region served by ACCRU has a population which includes approximately 5-7% minorities. Based on prior ACCRU studies involving similar disease sites, we expect about 5-7% of patients will be classified as minorities by race and about 50% of patients will be women. Expected sizes of racial by gender subsets are shown in the following table:

Accrual Estimates by Gender/Ethnicity/Race

Ethnic Category	Sex/Gender			
	Females	Males	Unknown	Total
Hispanic or Latino	1	1	0	2
Not Hispanic or Latino	36	37	0	73
Ethnic Category: Total of all subjects*	37	38	0	75
Racial Category				
American Indian or Alaskan Native	0	0	0	0
Asian	0	1	0	1
Black or African American	1	1	0	2
Native Hawaiian or other Pacific Islander	0	0	0	0
White	36	36	0	72
Racial Category: Total of all subjects*	37	38	0	75

Ethnic Categories: **Hispanic or Latino** – a person of Cuban, Mexican, Puerto Rico, South or Central American, or other Spanish culture or origin, regardless of race. The term “Spanish origin” can also be used in addition to “Hispanic or Latino.”

Not Hispanic or Latino

Racial Categories: **American Indian or Alaskan Native** – a person having origins in any of the original peoples of North, Central, or South America, and who maintains tribal affiliations or community attachment.

Asian – a person having origins in any of the original peoples of the Far East, Southeast Asia, or the Indian subcontinent including, for example, Cambodia, China, India, Japan, Korea, Malaysia, Pakistan, the Philippine Islands, Thailand, and Vietnam. (Note: Individuals from the Philippine Islands have been recorded as Pacific Islanders in previous data collection strategies.)

Black or African American – a person having origins in any of the black racial groups of Africa. Terms such as “Haitian” or “Negro” can be used in addition to “Black or African American.”

Native Hawaiian or other Pacific Islander – a person having origins in any of the original peoples of Hawaii, Guam, Samoa, or other Pacific Islands.

White – a person having origins in any of the original peoples of Europe, the Middle East, or North Africa.

17.0 Pathology Considerations/Tissue Biospecimens:

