- 1.228 A total of 9 deaths were reported within the safety evaluation period (within 30 days of the last dose of brentuximab vedotin) in 357 patients across the 6 phase 1 and phase 2 studies for which data are available. Two patient deaths (0.6%) were considered related to study treatment. One patient in Study SG035-0001 who received 3.6 mg/kg in phase 1 died due to febrile neutropenia and presumed septic shock. A second treatment-related death in Study SGN35-008A was attributed to pancytopenia, cytomegalovirus (CMV) infection, and intracranial hemorrhage. The remaining on-study deaths were primarily related to disease progression in sALCL patients.
- 1.229a Brentuximab vedotin has been shown to induce durable remissions in patients with HL both pre- and post-ASCT, and in patients with relapsed or refractory sALCL. PFS results comparing PFS with brentuximab vedotin to PFS from prior systemic therapy indicate that PFS is significantly prolonged with brentuximab vedotin for both HL and sALCL. A substantial number of HL and sALCL patients with B symptoms at baseline saw these symptoms resolve during treatment with brentuximab vedotin. In addition, the large majority of sALCL patients presenting with cutaneous lesions at baseline experienced resolution of these symptoms after receiving brentuximab vedotin. Study SGN35-009 is a phase 1, 2-arm, open label, multicenter study to evaluate the safety of brentuximab vedotin when administered in combination with standard therapy (ABVD) or a modified standard

(doxorubicin (Adriamycin), vinblastine, dacarbazine [AVD]). To date, patients have received doses of 0.6, 0.9, or 1.2 mg/kg brentuximab vedotin with standard doses of ABVD or 1.2 mg/kg brentuximab vedotin with AVD, depending upon cohort assignment. The combination regimens are administered on Days 1 and 15 of each 28-day cycle for up to 6 cycles of therapy. Each regimen evaluated a dose limiting toxicity (DLT) period, defined as any Cycle 1 toxicity requiring a delay of ≥ 7 days in standard ABVD or AVD therapy. No DLTs were observed. Enrollment of an expansion cohort further testing 1.2 mg/kg brentuximab vedotin plus AVD is now complete and treatment of enrolled patients is ongoing within this cohort.

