1.4 Safety in Subjects with Relapsed or Refractory Hematologic Malignancies

CA209039 Nivolumab, at 1 or 3 mg/kg, has an acceptable safety profile in subjects with relapsed or refractory hematologic malignancy, as demonstrated by the frequency, severity, and types of AEs, drug-related deaths, SAEs, and AEs leading to

discontinuation. The following were the key safety findings for 105 subjects treated with nivolumab monotherapy in CA209039 as of 15-Apr-2015:

- The most frequently reported drug-related AEs (> 10% of subjects) were fatigue (16.2%) and rash (10.5%). The majority were Grade 1-2 in severity.
- The most frequently reported drug-related SAE was pneumonitis (4.8%).
- Drug-related AEs leading to discontinuation were reported for 14.3% of subjects. The most frequently reported AE leading to discontinuation were pneumonitis (2.9%).
- The most frequently reported drug-related select AE categories were skin (19.0%), GI (9.5%), and pulmonary (9.5%). The most frequently reported ($\geq 5\%$ of total treated subjects) drug-related select AEs were rash (10.5%), pneumonitis (9.5%), pruritus (9.5%), and diarrhea (8.6%). Drug-related select AEs were mostly Grade 1-2 in all categories.
- Most deaths were due to disease progression. One death was reported due to study drug toxicity (The subject with non Hodgkin's lymphoma [small lymphocytic lymphoma] in the 3 mg/kg treatment group died due to Grade 5 pneumonitis with onset 10 days after the subject received the only dose of nivolumab).

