11.1 Response Considerations

Schedule of Evaluations: PET/CT scans are required at baseline for all patients. In addition to a baseline PET/CT scan, confirmatory scans should also be obtained post cycle 2 of chemotherapy and 6-8 weeks post cycle 8 of chemotherapy. During observation, CT scan should be obtained every 3 months during the first year to evaluate for disease progression.

Definitions for clinical response for patients with lymphoma are from the recently revised Cheson's et al criteria published in 2014, derived from the original criteria published in 2007. (Cheson et al, 2014)(Cheson et al, 2007). Up to six of the largest target nodes, nodal masses, or other lymphomatous lesions that are measurable in two diameters (longest diameter [LDi] and shortest diameter) should be identified from different body regions representative of the patient's overall disease burden and include mediastinal and retroperitoneal disease, if involved. A measurable node must have an LDi greater than 1.5 cm. Measurable extranodal disease (eg, hepatic nodules) may be included in the six representative, measured lesions. A measurable extranodal lesion should have an LDi greater than 1.0 cm. Lymph node measurements should be taken from the CT portion of the PET/CT, or other dedicated CT scans where applicable. Measurement of lymphadenopathy for purposes of assessing for PR will be determined by adding the sum of the products of the maximal perpendicular diameters of measured lesions (SPD). The PPD of a single node is sufficient to evaluate for PD (see Table 11.2). Measurable extranodal disease should be assessed in a manner similar to that for nodal disease. For these recommendations, the spleen is considered nodal disease. Disease that is only assessable (eg, pleural effusions, bone lesions) will be recorded as present or absent only, unless, while an abnormality is still noted by imaging studies or physical examination, it is found to be histologically and pathologically negative.

Response is based on PET/CT based on the revised 2014 Lugano Classification. (Cheson et al, 2014).

Progressive disease is based on either PET-CT based (PMD) or CT based (PD) response criteria. PET confirmation of progressive disease is per physician discretion.

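### Duration of response does not count death as an event and censors responders who have died, so its Kaplan-Meier curve overstates the proportion alive and still in response if any such death occurs

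*Combined protocol and SAP*

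**What the plan says.** Section 16.3 numbers two items 16.322. The first sets the DOR population: "Duration of response is defined for all evaluable patients who have achieved a response". Time runs from the first CMR or PMR "to the earliest date progression (PMD or PD) is documented. If a patient has not had disease progression, they will be censored" at the last disease assessment. The estimator is given as well: "The distribution of duration of response will be estimated using the method of Kaplan-Meier".

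The second item numbered 16.322 defines PFS. Its event is progression or death from any cause, and its censoring rule is "If a patient is alive and has not had disease progression, they will be censored on the date of their last disease assessment". Section 16.323, on overall survival, also makes being alive the condition: "If a patient is still alive, they will be censored on the date of their last follow-up".

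Section 11.1 says what progression means: "Progressive disease is based on either PET-CT based (PMD) or CT based (PD) response criteria". The criteria in Section 11.2 concern imaging and marrow findings and do not mention death. Section 2.23 only names DOR as a secondary goal. No section plans a competing-risk analysis.

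**The concern.** Followed as written, the DOR rule puts a responder who dies without documented progression in the same class as one who is alive and well at the last scan. Kaplan-Meier then assumes that the censored patient could still progress at the same rate as those who remain under observation. A dead patient cannot, so the curve is not the proportion alive and in response. Its complement is not the cumulative incidence of progression either.

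Such deaths are plausible here. Section 3.12 admits patients aged 60 or older, and younger patients with reduced cardiac, pulmonary or renal function or who refused chemotherapy. Section 13.4 observes them to 5 years from registration. Under footnote 5 of Section 4.0, scheduled CT during observation stops after the first year, so a patient can die with no recent scan.

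At stake is how durable the responses look. DOR is a named secondary endpoint, and Section 16.25 lists duration of response among the things weighed in any decision to terminate the study. The neighbouring PFS wording shows that the plan handles death where it means to.

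**Working it through.** The plan states no figure for DOR, so there is none to reproduce. The check is how far the curve as written departs from the proportion alive and in response.

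**Inputs**
- Evaluable patients: 56 (Section 16.21).
- Responders n: 45 (80% of 56 = 44.8) or 36 (65% of 56 = 36.4), using the alternative and null rates of Section 16.21.
- Progressions p by 24 months: 10 to 25 for n = 45, and 8 to 20 for n = 36. Assumed.
- Deaths without documented progression k: 1 or 2. Assumed, because the documents give no rate.
- Follow-up complete to 24 months, with no other censoring. Assumed.

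**Formulas**
- Proportion alive and in response = (n − k − p)/n.
- Kaplan-Meier with deaths censored lies between (n − k − p)/(n − k), if all deaths precede the progressions, and (n − p)/n, if all follow them.

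**Results**

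| n | k | p | Alive and in response | DOR curve as written | Overstatement (points) |
|---|---|---|---|---|---|
| 45 | 1 | 10 | 34/45 = 75.6% | 34/44 to 35/45 = 77.3–77.8% | 1.7–2.2 |
| 45 | 1 | 15 | 29/45 = 64.4% | 29/44 to 30/45 = 65.9–66.7% | 1.5–2.2 |
| 45 | 1 | 25 | 19/45 = 42.2% | 19/44 to 20/45 = 43.2–44.4% | 1.0–2.2 |
| 45 | 2 | 10 | 33/45 = 73.3% | 33/43 to 35/45 = 76.7–77.8% | 3.4–4.4 |
| 45 | 2 | 15 | 28/45 = 62.2% | 28/43 to 30/45 = 65.1–66.7% | 2.9–4.4 |
| 45 | 2 | 25 | 18/45 = 40.0% | 18/43 to 20/45 = 41.9–44.4% | 1.9–4.4 |
| 36 | 1 | 8 | 27/36 = 75.0% | 27/35 to 28/36 = 77.1–77.8% | 2.1–2.8 |
| 36 | 1 | 20 | 15/36 = 41.7% | 15/35 to 16/36 = 42.9–44.4% | 1.2–2.8 |

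**Check on another set.** Take 41 responders, the fewest successes that meet the final rule in Section 16.212, with 10 progressions and deaths censored at an earlier scan. For 1, 2 and 4 deaths the 24-month curve reads 75.2%, 74.8% and 74.0%, against 30/41 = 73.2%, 29/41 = 70.7% and 27/41 = 65.9% alive and in response. The gap is about 2, 4 and 8 points.

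**If such deaths were more common.** With constant hazards, and d the 24-month risk of death without progression, the overstatement is the DOR curve times d. For a curve at 70% and an assumed d of 2% to 15%, it is 0.70 × 0.02 = 1.4 to 0.70 × 0.15 = 10.5 points.

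**Anchors in the documents**
- Section 1.228, brentuximab vedotin, 357 patients: "Two patient deaths (0.6%) were considered related to study treatment". Scaled to 45 responders: 45 × 2/357 = 0.25 deaths.
- Section 1.4, nivolumab, 105 patients, one death from study drug toxicity: 45 × 1/105 = 0.43 deaths.
- Using the 0.96 to 2.22 points per death found for n = 45: 0.25 × 0.96 = 0.24 to 0.43 × 2.22 = 0.95 points on average.

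These anchors fit responders poorly. The nivolumab death was from pneumonitis "with onset 10 days after the subject received the only dose of nivolumab", whereas the first response PET-CT here falls just before cycle 3, after two 21-day cycles; that patient also had small lymphocytic lymphoma. One of the two brentuximab vedotin deaths was at 3.6 mg/kg, against a starting dose of 1.8 mg/kg here. Deaths not related to treatment are left out.

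**Against sampling error.** The 95% half-width is about 1.96 × √(S(1 − S)/45), which is 12.6, 14.0 and 14.4 points at S = 0.756, 0.644 and 0.422.

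**The case against.** The strongest reply is that the plan never promises a proportion alive and in response. It defines a start, an event, a censoring rule and an estimator, and two secondary endpoints may have different events. That stands in part: the difference from PFS is an inconsistency, not a contradiction, and a progression-only duration is coherent. But the plan does not label it so, and Kaplan-Meier is not clean on that reading either. With n = 45, k = 1 and p = 10, progression occurred in 10/45 = 22.2%, while one minus the curve gives 22.2% to 1 − 34/44 = 22.7%.

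Second, the deaths are reported elsewhere: in PFS, in OS and in adverse event reporting (Section 10.553). True, and it limits the harm, but it does not correct the DOR curve.

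Third, Section 10.331 asks for evidence when a death is attributed to progressive disease. If that evidence were accepted as documented progression, only deaths from other causes would be affected. No section says that it counts for DOR.

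Fourth, the overstatement does not hold at every instant. Censoring falls at the last scan, before the death, so the curve can briefly be the lower one. In 3,000 simulated data sets, 2,734 had at least one such death. The curve as written was lower at 6, 12, 18 or 24 months in 104 of these, and in none at the time of the last death.

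Fifth, the responder count is approximate. DOR starts at first response, which may be the PET-CT before cycle 3, so responders who later fail also enter. A larger n lowers the ceiling per death only modestly: 1/56 = 1.8 points if all 56 respond.

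Finally, counting every death would include one that follows other therapy or comes long after the last scan. The plan's own PFS rule does the same.

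**Conclusion.** The concern holds. The DOR rule censors responders who have died, and no other section corrects it. If any responder dies without documented progression, the curve overstates the proportion alive and still in response once the last such death has occurred. The overstatement is about 1 to 2 points per death with 45 responders, and 1.2 to 2.8 points for one death with 36. If none dies this way, the gap is zero. These figures assume complete follow-up to 24 months and the progression counts shown. Scaled from treatment-related deaths in the earlier studies, the average effect would be under 1 point, though those studies are a weak guide to responders here.

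The effect is small beside a half-width of about 13 to 14 points, but it is a bias in a known direction and not sampling error. It is confined to a secondary, descriptive endpoint. The primary endpoint, the decision rules, alpha and power are unaffected.

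**What to change.** Amend the first item numbered 16.322 so that DOR runs from first CMR or PMR to the earliest of PMD, PD or death from any cause. Censor only responders who are alive and progression-free, at their last disease assessment. This matches the PFS rule.

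If time to progression is what is wanted, name the endpoint that way and report the cumulative incidence of progression among responders with death as a competing event.

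Either change is about one sentence. It needs no new data, because PFS and OS already require the date of death. With the first option the reported duration may be slightly shorter. The choice should be made before the analysis, so that it does not depend on how many such deaths occur.
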